### 10.2.4. Clinician Focused Qualitative Assessments

A series of questionnaires will be administered to the clinicians involved in the care of study participants across the hospital. Each questionnaire will be focused on a subset of clinicians. It is likely that the same clinician may provide care for multiple study participants over the course of the study. Eligible clinicians should complete the focused questionnaire(s) only once if they provide care to more than one study participant. If the questionnaire has a Pre/Post component, both the Pre and the Post should be completed only one by each eligible clinician.

Eligible clinicians will be provided with the clinical team questionnaire information sheet during the informed consent process. If the clinician is willing to consider participation, the clinician will provide consent by completing the questionnaire and returning to the study team. A Clinician Participant Log will be used to capture clinicians who participated in the clinician focused qualitative assessments.

This document is electronically controlled. Printed copies are considered uncontrolled.

**Perception Questionnaire for Prescribing Clinicians (PRE)**

Eligible clinicians will be any clinician who ordered telemetry monitoring for the study participant. The questionnaire should be administered to the clinician after enrollment of the subject, but if the clinician is not available at the time of enrollment it is acceptable to administer the questionnaire during the inpatient period.

**Perception Questionnaire for Prescribing Clinicians (POST)**

Eligible clinicians will be any clinician who ordered telemetry monitoring for the study participant. The POST questionnaire should be administered at the end of the SM phase after all subjects have completed study participation.

**Telemetry Utilization Questionnaire for Clinicians (PRE)**

Eligible clinicians will be any telemetry clinician who provides inpatient care for the study participant. Other eligible clinicians who may not provide direct care to participants but have visibility into hospital resource utilization impacting the flow of patients during the study period will be eligible. Examples clinicians include ED physicians/nurses, intensivists, critical care nurses, and hospitalists. The PRE questionnaire should be administered to the clinician after enrollment of the subject, but if the clinician is not available at the time of enrollment it is acceptable to administer the questionnaire during the inpatient period.

**Telemetry Utilization Questionnaire for Clinicians (POST)**

Eligible clinicians will be any telemetry clinician who provides inpatient care for the study participant. Other eligible clinicians who may not provide direct care to participants but have visibility into hospital resource utilization impacting the flow of patients during the study period will be eligible. Examples clinicians include ED physicians/nurses, intensivists, critical care nurses, and hospitalists. The POST questionnaire should be administered at the end of the SM phase after all subjects have completed study participation.

**Clinical Team Satisfaction Questionnaire**

Eligible clinicians will be any clinician who provides inpatient care to the study subject participating during the SM phase of the study and interacts with the study devices, the Vital Sync™ IM & VPMP and the BioModule. The satisfaction questionnaire should be administered to clinicians at the end of the SM phase after all subjects have completed study participation.

**10.3. Subject Screening**

Subjects who have an order placed for telemetry monitoring at the study site will be pre-screened as potential subjects for the study. In order to do so, only the existing information obtained per standard routine medical procedures will be used. No study-specific screening procedures, activities or questionnaires will be performed during the pre-screening. The Screening and Enrollment Log will capture both pre-screened and screened subjects. The log will also capture reasons why eligible pre-screened subjects did not participate in the study.

Potentially eligible subjects will be provided with detailed information about the study during the informed consent process. If the subject is willing to consider participation, written informed consent must be obtained.

This document is electronically controlled. Printed copies are considered uncontrolled.

**Confidential**

Protocol #: COVMOPO0561

Rev E 09AUG2017

After informed consent, if a subject does not meet the inclusion/exclusion criteria, the subject will be considered a screening failure and may not participate in the study. If the subject is determined to be ineligible for the study, the reason will be documented on the Screening and Enrollment Log.

#### **10.4. Subject Consent**

Informed consent must be obtained before a subject is enrolled in the study and/or before any study-specific procedures are initiated.

Potential subjects expressing an interest in participating in the study will be given written and oral information about the study, their rights as a subject in a research project, as well as a copy of the subject informed consent form. The potential subject will be encouraged to discuss participation in the study with their support network (family, friends, ordering physician). Any study-related questions posed by the potential subject will be answered. Potential subjects are given adequate time to consider their participation.

Potential subjects who then wish to participate and who appear to meet the inclusion/exclusion criteria will be asked to sign and personally date the Informed Consent Form. The investigator and or an authorized designee will also sign and personally date the Informed Consent Form. The signed original informed consent is maintained in the investigator's records, and a copy given to the subject.

The Informed Consent Form should cover all essential information per the protocol, Good Clinical Practices (GCP), release of hospital billing data, and the applicable regulatory requirements.

If the Informed Consent Form is amended/updated throughout the life-cycle of the study, study subjects may be asked to re-consent by reviewing, signing and personally dating the updated Informed Consent Form. A copy of the amended/updated Informed Consent Form will be provided to the subject.

#### **10.5. Blinding**

No blinding will occur during the course of the study.

#### **10.6. Randomization**

No randomization will be used during the course of the study. Assignment to a monitoring arm will be determined by the phase status of the study. During the TM phase, all subjects will be assigned to the TM group. During the SM phase, all subjects will be assigned to the SM group.

#### **10.7. Assessment of Safety**

Methods and timing for assessing, recording, and analyzing safety parameters, including adverse events are described in section 12.

#### **10.8. Recording Data**

The investigator will clearly mark the clinical records to indicate that the subject is enrolled in this clinical study.

This document is electronically controlled. Printed copies are considered uncontrolled.

**Confidential**

Protocol #: COVMOPO0561

Rev E 09AUG2017

Subject's medical record will be used as source documents. Additional source worksheets will serve as supplemental source documentation when a data field is not in the subject's medical record.

The investigator will allow inspections of the study site and documentation by Clinical Research and audit personnel from Medtronic or designee, IRB, external auditors, or representatives of regulatory authorities. The purpose of these inspections is to verify and corroborate the data collected on the eCRFs. In order to do this, direct and secure access to medical or clinical records and billing databases will be necessary.

The investigator must ensure accuracy, completeness and timeliness of the data reported in the eCRFs and in all other required reports. Data reported on the eCRFs which are derived from source documents, such as patient medical records, must be consistent with the source documents or the discrepancies need to be justified in a documented rationale, signed and dated by the Principal Investigator, to be filed in the subject file. All baseline and medical history data must be derived from source documents. Only authorized persons can complete eCRFs and record observation. Training will be provided to site personnel on the use of data collection tools, as described in section 8.5. A final version of eCRFs will be provided to the investigation site when the investigational site has been declared ready for the study.

Sponsor study personnel will review collected data and create data queries for missing data that impacts data analysis. Queries will be sent to the investigator or appropriate support staff for resolution within a preferred 5 business day period. Where copies of the original source document as well as print outs of original electronic source documents are retained, these shall be signed and dated by a member of the investigation site team with a statement that it is a true reproduction of the original source document.

## 10.9. Deviation Handling

The investigator is required to conduct this study in accordance with the CIP, IRB requirements and applicable regulations.

A CIP deviation is defined as an event when the investigator or site personnel did not conduct the study according to the CIP or the clinical trial agreement. Thorough documentation of all deviations in source documents and transcription to eCRF is required, along with notification to your sponsor contact. Additionally, the site must complete the Deviation Log found in the ISF.

Major deviations are associated with subject safety or data integrity. They are defined as deviations with respect to:

- Patient informed consent procedure
- Patient eligibility criteria at the time of initial screening/enrollment
  - Deviations of daily tracking of eligibility procedures are not a major deviation
- Study data collection and reporting
- SADE reporting

All deviations and reasons to deviate from the study protocol must be reported prior to deviation when planned or promptly after occurrence when unplanned to the sponsor regardless of whether medically justifiable, pre-approved by the sponsor, or taken to protect the subject in an emergency.

This document is electronically controlled. Printed copies are considered uncontrolled.

## 10.10. Subject Withdrawal or Discontinuation

During the course of this study, subjects may elect to be or may be withdrawn from further treatment for any of the following reasons:

- The subject may withdraw from the study for any reason without prejudice
- The clinician or investigator may terminate the study at their discretion
- Subject is prescribed additional continuous monitoring after enrollment
- Within the first 12 hours of study participation, subject is discharged from hospital or removed from the study for any reason
- Subject no longer meet study inclusion/exclusion criteria
- Technical issues that prevent continuous data collection from the Vital Sync™ IM & VPMP
- Sponsor terminates the study
- Other

Subjects may withdraw from the study at any time and for any reason. If a subject officially withdraws from the study, the investigator will document the reason and collect final outcomes data from the subject's medical record. No additional follow-up will occur for withdrawn subjects.

Subjects may only be replaced if they are a screen failure OR are withdrawn from the study during the first 12 hours of enrollment for any reason.

Withdrawal or discontinuation from the study will not affect the subject's regular care/hospitalization in any way.

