### 10.1. Monitoring Group Assignment

#### Telemetry Monitoring (TM) Group, Control

The TM group will serve as the control group and will be monitored via the site's standard of care telemetry practice/protocol. Subjects will continue to be enrolled in the study if subjects are transferred to medical-surgical unit after initial period of TM. Subjects will be tracked daily to confirm continuing eligibility for the study. Temporary alternate monitoring modalities will be allowed per the discretion of the Investigator. If subject no longer meets eligibility criteria, the subject should be withdrawn and study completion date will be the date the subject became ineligible not the date the study team discovered the ineligibility.

If a subject is transferred to another hospital unit or telemetry is discontinued, subject will continue to be enrolled in the study.

If subject is transferred to ICU, there will be an exception to the requirement of tracking daily continuing eligibility. It is expected for additional care and monitoring to be administered during the ICU stay and AHA indication to change. Once subject is transferred from the ICU back to a lower acuity unit, eligibility criteria will be reassessed and documented. If subject no longer meets eligibility criteria upon return to

This document is electronically controlled. Printed copies are considered uncontrolled.

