### **Surveillance Monitoring (SM) Group**

Subjects in the SM group will alternatively be admitted to a medical surgical unit and placed with the study device following study enrollment. Hospital staff will utilize SM for the duration of study enrollment.

The sponsor and investigator will collaborate to implement the SM strategy. This implementation could include a variety of strategies based on the site's facilities, staffing resources, and IT infrastructure. The Vital Sync™ IM & VPMP conveys physiologic data, waveforms, and will provide visual alerts and annunciation alarms. Alert and alarm thresholds will be customized as needed to align with the hospital's protocols. Data from the remote monitoring platform will be accessed at a central workstation, a workstation on wheels, a bedside tablet, and/or smartphones/tablets.

Subjects will be tracked daily to confirm continuing eligibility for the study. Temporary alternate monitoring modalities will be allowed per the discretion of the Investigator. If subject no longer meets eligibility criteria, the subject should be withdrawn and study completion date will be the date the subject became ineligible not the date the study team discovered the ineligibility.

If a subject is transferred to another hospital unit, subject will continue to be enrolled in the study. However, the subject will be removed from SM during the transfer including placement of BioModule. When the subject transfers back to the medical-surgical unit, SM should resume as soon as reasonably possible per discretion of the Investigator until discharge from the hospital or end of study enrollment.

If subject is transferred to ICU, there will be an exception to the requirement of tracking daily continuing eligibility. It is expected for additional care and monitoring to be administered during the ICU stay and AHA indication to change. Once subject is transferred from the ICU back to a lower acuity unit, eligibility criteria will be reassessed and documented. If subject no longer meets eligibility criteria upon return to lower acuity unit, the subject should be withdrawn from the study. If subject meets eligibility criteria daily, subject will resume SM procedures and daily tracking of eligibility criteria.

[figure not shown]
This document is electronically controlled. Printed copies are considered uncontrolled.

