**Confidential**

Protocol #: COVMOPO0561

Rev E 09AUG2017

- Any adverse events noting mild or moderate physiological deterioration
- Any adverse event whose relationship to the study device is: possible, probable, definite, or unknown/ impossible to determine, regardless of what the event may be.
- All SAEs, of any relationship, meeting definition in section 12.2 of the CIP must be reported.

The recording of adverse events for all enrolled subjects begin after the study devices are attached and ends with the subject's completes study enrollment. Completion is defined by when a subject is discharged from the hospital, completes 30 day ( $\pm$  2 days) enrollment period, or if the subject is withdrawn from the study for any reason.

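### A technical failure of the study system can end an SM subject's study follow-up, while a TM subject whose telemetry stops stays enrolled; safety time, and possibly length of stay, can be lost from SM only

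*Protocol*

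**What the plan says.** Protocol 10.10 gives a list of reasons for which "subjects may elect to be or may be withdrawn from further treatment". One is "Technical issues that prevent continuous data collection from the Vital Sync™ IM & VPMP". The list has no counterpart for failure of the telemetry system. Other reasons, such as "Subject is prescribed additional continuous monitoring after enrollment", loss of eligibility and a catch-all, are open to both groups.

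Protocol 10.1 has a separate rule for TM: "If a subject is transferred to another hospital unit or telemetry is discontinued, subject will continue to be enrolled in the study". It names no reason for the discontinuation. The SM part of 10.1 has the transfer half of that rule, "If a subject is transferred to another hospital unit, subject will continue to be enrolled in the study", and says the sensor comes off during the transfer and SM resumes on return. It does not say what happens to enrolment if SM stops for a technical reason.

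On data after withdrawal, Protocol 10.10 says the investigator "will document the reason and collect final outcomes data" from the medical record, and then: "No additional follow-up will occur for withdrawn subjects". SAP 7.4 repeats both statements. Protocol 12 and SAP 7.10 end adverse event recording at discharge, at the end of the 30-day period, "or if the subject is withdrawn from the study for any reason".

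The primary analysis uses all evaluable data (Protocol 13.3, SAP 7.1.3 and 7.2). Neither document defines *evaluable*.

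**The concern.** The study asks whether SM can stand in for telemetry. Technical failure of SM is one consequence of making that switch, and Protocol 11.1 foresees it: radio interference, a patient out of range and network failure are listed as causes of lost monitoring. The time after such a failure therefore belongs in the SM experience. Under 10.10 it can be removed by withdrawing the subject. Under 10.1 the TM subject who comes off telemetry keeps contributing.

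Two things are at stake. The first is safety: recording of adverse events ends at withdrawal, so SM can lose the period in which the substitute was not working. The second is the primary endpoint. If failure can occur at any point in the stay, longer stays are more exposed to it. Dropping those subjects, or stopping their LOS clock at withdrawal, would shorten SM LOS and favour both the non-inferiority claim and the superiority test that follows it.

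**Working it through.** **The rules side by side**

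| Event | SM | TM |
|---|---|---|
| Moved to another unit | stays enrolled (10.1) | stays enrolled (10.1) |
| Monitoring stops for a technical reason | may be withdrawn (10.10) | not named separately; stays enrolled if telemetry is discontinued (10.1) |
| Adverse events after withdrawal | not recorded (12) | not recorded (12) |

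The adverse event rule is the same in both groups. The difference lies in who can reach it. This part of the point needs no assumption about how LOS is analysed.

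**The plan's sample size**

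Protocol 13.1 and SAP 6 give a coefficient of variation of 0.65, a margin of 0.2 on the mean ratio (read as 1.20), 132 per group, power above 80% and a significance level of 0.05.

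- Log-variance: ln(1 + 0.65²) = 0.352, so the log-scale SD is 0.594.
- n = 2 × 0.352 × (1.645 + 0.842)² / (ln 1.20)², which rounds up to 132 per group. Power at 132 is 80.2%.

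The plan's figure reproduces at one-sided 0.05. At one-sided 0.025, which matches the general two-sided 0.05 rule in Protocol 13.3, it would be 167.

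**LOS bias if technically withdrawn SM subjects are excluded (closed form)**

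Assumptions: log-normal LOS, a small constant failure hazard in SM only, and a fraction f of SM removed. The documents give no failure rate.

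- Removal is then proportional to LOS, so the removed subjects' mean log-LOS is 0.352 above the SM mean (a factor of 1.42).
- The retained SM mean shifts by −f × 0.352 / (1 − f).
- Standard error: √(2 × 0.352 / 132) = 0.0731.
- False non-inferiority at a true ratio of 1.20: Φ(|shift| / 0.0731 − 1.645).

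| f | Shift | 1.20 appears as | One-sided 0.05 | One-sided 0.025 |
|---|---|---|---|---|
| 0 | 0 | 1.20 | 5.0% | 2.5% |
| 5% | −0.0185 | 1.18 | 8.2% | 4.4% |
| 10% | −0.039 | 1.15 | 13.4% | 7.7% |

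**Simulation**

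This used the same LOS model, 154 per group before technical loss (220 × 0.7), a log-scale t-test and 8,000 trials per case. The false non-inferiority columns are at a true ratio of 1.20 and one-sided 0.05.

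| Failures per mean stay (assumed) | SM withdrawn | LOS kept to discharge | Excluded | LOS cut at withdrawal |
|---|---|---|---|---|
| 0.05 | 5.7% | 5.0% | 8.8% | 19.9% |
| 0.1 | 11.1% | 5.0% | 14.0% | 46.6% |
| 0.2 | 20.4% | 5.0% | 28.9% | 87.6% |
| 0.3 | 28.6% | 5.0% | 45.7% | 99.2% |

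With no true difference, a false finding that SM is shorter rises from 2.6% to between 4.0% and 25.6% (excluded) or between 10.0% and 92.8% (cut) over the same range. If LOS runs to actual discharge for everyone, withdrawal changes nothing and the required number stays at 132 per group.

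**The case against.** A reader might infer that failed SM subjects and long SM stays do leave the comparison, and that the primary result is therefore biased. The documents do not support that, for these reasons.

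- Withdrawal is permissive. Nothing requires the site to withdraw a subject when the system fails.
- No section removes withdrawn subjects from the LOS analysis. Protocol 10.10 and SAP 7.4 call for final outcomes from the medical record, and admission-to-discharge time can be read from that record.
- A system failure does not vanish from the data. Malfunctions are device deficiencies (Protocol 12.2) and are documented on inpatient days and at the end of the study (10.2.2, 10.2.3).
- Stopping telemetry may be an ordinary care decision, so the two events are not exact counterparts. The documents do not mention technical failure of telemetry.
- The constant hazard is an assumption. If failures cluster at set-up, loss is largely unrelated to LOS and the bias shrinks. Routine sensor change-outs are not failures.

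All of this stands, and it limits the LOS part to a conditional risk. It does not remove that risk. Protocol 13.1 inflates 132 to 220 partly for withdrawals, which makes sense only if some withdrawn subjects are expected to contribute no LOS. The final-outcomes sentence applies to a subject who officially withdraws, and it directly follows a sentence on subjects choosing to leave. Whether it covers a withdrawal by the site for a technical fault is unclear. Nor does any of it answer the safety part, because adverse event recording ends at withdrawal whatever happens to LOS.

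**Conclusion.** The point holds in two parts of different strength.

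The safety part follows from the text. Only SM has a technical ground for withdrawal, TM subjects stay enrolled when telemetry is discontinued, and withdrawal ends adverse event recording. SM time after a system failure can therefore leave the comparison while TM time off telemetry remains. How much time is lost cannot be sized from the documents.

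The LOS part is conditional on exclusion or truncation, which the documents neither state nor rule out. Under exclusion, constant hazard and an assumed 5% or 10% of SM removed, false non-inferiority at a true ratio of 1.20 goes from 5% to about 8% or 13% (one-sided 0.05). Truncation would be worse. In both scenarios the direction favours SM. With LOS kept to discharge the bias is nil. These figures illustrate sensitivity; they do not predict what this trial will show.

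The matter should be corrected, because the remedy is small and the ambiguity bears on both safety and the primary endpoint.

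**What to change.** **Protocol.** Reconcile 10.10 with 10.1 so that loss of SM data collection for technical reasons is not a ground for leaving the study. As in TM, the subject stays enrolled in the assigned group, with LOS, rapid response team calls, code blue, ICU transfer and adverse events collected to discharge or the end of the study period. This concerns study follow-up only; whether the device is used remains a matter for the site. Device deficiencies are already recorded, so add only the start and stop times of the interruption.

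**SAP.** Define the primary LOS set as every subject who started monitoring, with LOS to actual discharge whatever the reason for withdrawal. This also prevents the catch-all and investigator-discretion grounds from reopening the gap. Report withdrawals by reason and group.

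**Cost.** A short protocol amendment and a few SAP sentences. The data come from the medical record and the daily tracking already planned, and the required number per group does not change. The downside for the sponsor is that the SM result will include time off the device and may look slightly less favourable.
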